## **APPENDICES**

## I. INTRODUCTION, BACKGROUND & RATIONALE

Invasive cardiac catheterization-based procedures are done via transradial (TRA) or transfemoral access (TFA). These procedures are important in the diagnosis and treatment of coronary artery disease. Transradial access (TRA) for invasive cardiac catheterization procedures has gained significant popularity around the world compared with the transfemoral access. And in fact, and as early as 2016, the European Society of Cardiology guidelines have given transradial access its highest recommendation (Class I A) over femoral access. The most compelling reason for adopting TRA is the increased patient safety that results from the potential elimination of access site bleeding and vascular complications. In addition, TRA is associated with early sheath removal, improved patient comfort, faster recovery, and lower costs in comparison with transfemoral access.

One of the largest concerns of TRA vs TFA, is the occurrence of radial artery occlusion, which is in part related in part to prolonged radial artery compression time with such devices as the trans-radial air-bladder bracelet (TR band [TRB] (Terumo, Tokyo, Japan). Given that safe reduction in compressions times may reduce the risk of radial artery occlusion, we have previously shown that the adjunctive use of a potassium ferrate hemostatic patch (PFHP, Statseal Advanced RAD, Biolife, Sarasota, FL) with a TRB reduces composite overall complications and time to TRB deflation (68±15 vs 138 ± 62 min, P<0.001) as compared to use of the TRB alone. The PFHP contains potassium ferrate on a bed of hydrophilic polymer. The polymer rapidly dehydrates and concentrates blood solids, while the potassium ferrate agglomerates the solids & proteins together, forming a seal to the wound to stop bleeding. Beneath the seal, blood solids and proteins continue to concentrate and stack down, promoting hemostasis at the arteriotomy site without components of the PFHP reaching the vessel.

While the TRA provides the ability to perform a broad range of diagnostic and interventional cardiovascular procedures, there are clear limitations to its use. Compared with TRA, transfemoral provides an easier access, less radiation time, and less contrast agent administered to the patient. Importantly, there is still a growing need for TFA in the setting of advancements of structural heart procedures (e.g. use of transcatheter aortic valve replacements) and mechanical circulatory support (e.g. use of left ventricular assist devices such as the Impella). Further, TFA plays an important role on peripheral endovascular interventions such as angioplasty, stenting, atherectomy, and thrombectomy. In these scenarios, TFA cannot be replaced by TRA. Additionally, operators will often times require TFA during the same index or later procedure in the setting of TRA failure due to a variety of reasons including patient discomfort and inability to deliver procedural equipment.

Two of the most common standard of care methods for TFA hemostasis are the suture-mediate closure device Perclose ProGlide™ system (Abbott Vascular, CA, USA) and the collagen-plug mediated Angio-Seal™ (St. Jud Medical) devices. While first generation TFA closure devices were reported to increased vascular complications in comparison to manual compression, closure devices overall have emerged as a safe and effective alternative method to manual compression. Larger registry studies have suggested equivalence of the Perclose™ (Abbott Laboratories) arterial closure device to manual compression, while the Angio-Seal™ (St. Jude Medical) device has shown a decrease in manual compression time following percutaneous coronary intervention (PCI). More recently, a separate meta-analysis of randomized trials showed a strong trend for a reduction of major vascular complications with the use of Angio-

Seal™ following PCI, whereas Perclose™ has had equivalent vascular complication compared to manual compression.

The Angio-Seal™ arterial closure device has a bioabsorbable intraluminal anchor and extraluminal collagen plug. More recent iterations of the device now have a 37% greater collagen footprint at the site of arteriotomy. Re-access of the femoral artery is not recommended for at least 3 months in fear of possible embolization of the collagen plug. The Perclose Proglide™ utilizes a monofilament suture, which facilitates knot delivery and helps to retain knot tensile strength. Given, the suture mechanism, TFA at or near the same site is not contraindicated. When comparing these two devices in PCI patients, a recent randomized study showed that while there is no significant difference in major vascular complications between the two devices, time to hemostasis was shorter (5.3 vs. 46.8 min,  $P < 0.01$ ) and time to ambulation was longer (261 vs. 334 min,  $P < 0.05$ ) with the Angio-Seal VIP™ device compared to the Perclose Proglide™.

## THE CLINICAL NEED

Despite the use of both the Perclose™ and the Angio-Seal™ commonly for TFA closure there has been no clinically established time to ambulation post-deployment. While time to ambulation varies widely based on operator in both diagnostic and PCI catheterizations (which require anticoagulation), the Perclose™ instructions for use indicate that a patient may ambulate 2 hours after their device is deployed if using a 5-8F sheath and similarly Angio-seal™ recommends ambulation 2 hours after deployment. Particularly for Perclose™, which could otherwise be considered ideal over Angio-Seal™ given its properties allowing for immediate re-access, reducing time to hemostasis and ambulation would be important. To this end, the utility of PFHP would be of particular interest in those undergoing TFA with a Perclose™. While the PFHP have been shown to be safe and decreased time to hemostasis when used in conjunction to manual compression, it has not been studied in conjunction with a closure device. PFHP in conjunction with manual pressure is most commonly used in the catheterization lab when a contraindication to a closure device exists such as severe arterial disease, but may also improve time to hemostasis and ambulation when used in conjunction with a Perclose™. Establishing a safe expedited protocol with use of a closure device and a PFHP could result in multiple favorable clinical and hospital outcomes:

- Decreased femoral artery hemostasis times
- Decreased incidence of oozing, bleeding or hematoma complications
- Facilitate arterial site management to the more specialized catheterization lab staff/personnel that are better trained to recognize complications
- Decreasing time in the cath lab trying to obtain hemostasis, therefore increasing case throughput and number of cases per day
- Decreasing the workload to the staff by virtue of shortened band in place times and improve procedural throughput.
- Facilitate greater patient comfort resulting from decrease supine time and faster wound healing
- Facilitated faster discharge time allowing for more beds to be available during time of critical bed shortages.

Through our pilot study of 180 patients and multicenter randomized clinical trial of 443 TRA patients we were able to show the capabilities of an adjunct PFHP to an additional standard of

care closure device to achieve many of those favorable clinical outcomes. We showed time to complete TRB deflation was  $66 \pm 14$  min with the PFHP vs.  $113 \pm 56$  min for TRB alone ( $P < 0.001$ ) in the setting of no minor rebleeding in the TRB + PFHP group. Furthermore, among PCI patients, time to TRB deflation ( $68 \pm 15$  vs  $138 \pm 62$  min,  $P < 0.001$ ) and composite complications [10.0% vs. 24.2%,  $p=0.04$ ] were reduced with the PFHP.

Thus, the Statseal was demonstrated to facilitate a rapid deflation protocol with the TRB, allowing for an earlier discharge, without evidence of significantly increased complication of hematomas or radial artery occlusion. The present study is designed to evaluate the use of Statseal in the TFA population in conjunction with use of the Perclose™ TFA closure device.

Additionally, the TFA is the preferred approach for transcatheter aortic valve replacement (TAVR). In contrast to the 6Fr TFA, TAVR procedures require large bore catheters of 14 to 16 Fr in many circumstances. There has been widespread adoption of the Perclose™ TFA closure device, with many institutions, including our own using a single Perclose closure in order to hemostasis. The present study is designed to evaluate the use of Statseal in the TAVR TFA population in conjunction with use of a single Perclose™ TFA closure device.

## **II. DESCRIPTION OF THE STUDY DEVICE:**

A new compound – potassium ferrate, in combination with a hydrophilic polymer which is formed into a disc when compressed - has been used in conjunction with hemostasis bands to shorten compression times. This product (trade name StatSeal Advanced) is an FDA approved product comprised of a topical hydrophilic polymer and potassium ferrate disc, [Photo 1] formed by compression of the compound.

[figure not shown]

Photo 1: StatSeal Advanced Disc

When in the direct contact with even a small amount of blood, the compound forms an occlusive seal through simultaneous iron-mediated agglomeration of blood solids/proteins and rapid dehydration of the blood. Seal formation is independent of the clotting cascade, facilitating sealing regardless of anticoagulation / antiplatelet status of the patient. Following cessation of pressure being applied to the site, the remnants of StatSeal form what resemble a 'scab', and remains in place for 24 hours, covered with a band-aid or Tegaderm patch.

## INDICATION FOR USE

StatSeal Advanced is a commercially available product in the United States, and is indicated for use on patients in whom the radial or femoral artery has been used to gain vascular access for a cardiovascular procedure.

## DEVICE STORAGE AND ACCOUNTABILITY

StatSeal Advanced is provided in a sterile, foil pouch to protect it from humidity / moisture. As

with most medical products, it should be stored in a cool, dry, secure environment. StatSeal Advance will be provided at no charge by the manufacturer for use in the study.

Damaged devices will be returned to the manufacturer (Biolife, LLC, Sarasota,FL). All unused devices may be retained by the site for continued use, if they so choose.

### **III. STUDY OBJECTIVE(S)**

The primary objectives of this study are to evaluate the performance of StatSeal Advanced used in conjunction with the Perclose™ (SS) as compared to the Perclose™ without SS (PC) relative to:

TAVR Outcomes:

1. Primary outcome: Time to Hemostasis (TTH)
2. Secondary outcome: The incidence of access hematomas

Time to hemostasis (TTH) is defined as the time period required to achieve hemostasis, beginning at the time at which the Perclose™ is deployed to the access site to when no additional bleeding is appreciated..

Hematoma are defined as being <5 cm, 5-10 cm, and >10 cm. The physician on the study team will make the assessment for the incidence and size of the hematoma based on physical exam and /or diagnostic imaging including ultrasound. Hematoma assessment will be done in multiple incidences: at the time of Perclose deployment while in the catheterization lab, at the time of admission to the recovery unit by the TAVR team, and at the time of admission to the inpatient service for overnight monitoring. While in recovery the patient will be evaluated by the staff for 15 minutes for one hour, every 30 minutes for the next hour, and every hour for the subsequent four hours (for a total of 6 hours post-procedure while in the recovery unit). While admitted for overnight monitoring (at least for a 24 hour period), the patient will have their site evaluated every 4 hours until the 24 hours period has been reached.

### **IV. STUDY DESIGN AND METHODOLOGY**

#### **STUDY DESIGN**

This study is a physician initiated, prospective, observational, two arm, randomized study to be performed at one academically affiliated with high catheterization volumes. Enrollment will continue at each site on discretion of the investigators until at least 50 patients are enrolled. Clinicians will perform the catheterization in accordance with local standard practice, with no minimum amount of anticoagulation required during the procedure.

#### **STUDY METHODS:**

Patient Selection Criteria Study subjects will be identified in their outpatient appointments during their appointments with the structural heart team prior to their TAVR procedure.

Inclusion Criteria:

- Left heart catheterization with plans for delivery of a 14-16 Fr TAVR system

Exclusion Criteria:

Candidates for this study will be excluded if any **one** of the following criteria is true.

- Use of a hemostasis method or device besides Perclose™ (Perclose may not be used in situations of heavy calcification, presence of dissection, etc).
- Use of an anticoagulant other than unfractionated heparin or bivalirudin during the procedure.
- Any use of glycoprotein inhibitors or cangrelor.
- Use of sheathless guides.
- Any anticipated need for continued anticoagulation post-catheterization, including extended bivalirudin infusion.
- Any active treatment with oral anticoagulants continued during course of procedure.
- Presence of arteriovenous dialysis fistula in the ipsilateral leg.
- Any physical deformity or trauma / injury of the leg that would prevent proper placement or function of the hemostasis band.
- Inability of the patient to personally consent for the study. (no surrogate consent)
- Cardiogenic shock, emergent procedures (high risk myocardial infarctions), or any clinical instability as assessed by the physician performing the procedure.

Transfemoral Catheterization Procedure

TFA Cardiac Catheterization will be performed according to local practice standards with use of a 14-16 Fr sheath during a TAVR procedure.

Patients will have their activated clotting time measured prior to sheath removal and at least 5 minutes following the initial dose of anticoagulant. Additional activated clotting time measurements for PCI would be expected as part of routine practice but not recorded. Vasodilators (nitroglycerin, verapamil) will be administered in accordance with local practice.

Timing of Subject Enrollment

A subject will be consented into the study prior to the administration of sedation prior to the procedure, and randomized at the conclusion of a successful deployment of the Perclose device (after all anticoagulation and antiplatelet medication decisions have been made), at which time placement of the assigned device will occur. Eligibility for the study will be assessed at this time and the subject will have to meet all of the inclusion criteria and none of the exclusion criteria.

Randomization will be performed by means of sealed envelopes in randomization blocks of 25. Each envelope will be labeled by patient number containing device designation. Device designation in the envelopes will be random in occurrence. When a patient is officially enrolled (after Perclose™ deployment) the envelope corresponding to that patient number in the Study Patient log will be pulled, opened, and the assignment revealed.

End of Study Status / Effect of Withdrawals:

A subject will have completed the study when one of the following events is documented:

1. The patient is successfully enrolled, treated with a Perclose™, and completes all required follow up.

2. A subject withdraws consent to participate. Patients who withdraw from the study will have their data included to the extent allowable by law. As all study related procedures are expected to be completed on the day of the procedure or day after, subject withdrawal is not considered likely.

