### **VI. STUDY STATISTICAL PLAN:**

This is a physician initiated, prospective, randomized, two-arm study, to be conducted at high-

volume academically affiliated centers with the cath lab staff having a (minimum) ten case experience using StatSeal Advanced. The primary analysis will be by intention-to-treat methodology.

A sample size of 50 patients is sufficient to have >90% power to detect an average expected difference of 10 minutes in time (5 min vs 15 min) to hemostasis (different primary outcomes compared to 6F study) between the SS and Perclose groups, using a two-sided alpha of 0.05. A standard deviation of 10 minutes is assumed, which will be the additional time for manual compression if any site oozing/bleeding is seen after the initial compression. A different standard deviation time was assumed given larger bore access for TAVR TFA access.

Descriptive summary statistics will be presented for all study variables. Continuous variables will be displayed as means with standard deviations and medians with 75th and 25th percentiles. Categorical variables will be summarized as frequencies with their respective percentages with two-sided 95% exact confidence intervals of the percentages. Statistical comparisons for continuous variables will be performed using the Student's t test or Mann-Whitney U test, as appropriate. Comparisons for categorical variables will be performed using the Chi square test or Fisher exact test, as appropriate. A two-sided P value of 0.05 will be considered statistically significant.

A single multivariate logistic regression will be reported for the safety outcome of hematoma formation. In order to create this model, study arm and variables known to place patients at higher risk for hematoma formation will be tested in univariate analysis for the primary safety outcome. Those variables with a P<0.10 will be included in backwards stepwise regression modeling to obtain a final model. Similar to our prior published study, the following variables will be analyzed: Age, sex, weight, hypertension, diabetes, creatinine, pre-procedural INR, pre-procedural platelet level, heparin dose given, PCI, last ACT prior to procedural end, and last SBP prior to procedural end.

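### The primary time-to-hemostasis (TTH) comparison leaves out a pre-randomisation ACT that the protocol already requires; adjusting for it would cost little and may add precision

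*Combined protocol and SAP*

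**What the plan says.** - **When ACT is measured.** Section IV (Transfemoral Catheterization Procedure): "Patients will have their activated clotting time measured prior to sheath removal and at least 5 minutes following the initial dose of anticoagulant". Section V defines the end of the procedure as sheath removal.
- **When patients are randomised.** Section IV (Timing of Subject Enrollment): patients are "randomized at the conclusion of a successful deployment of the Perclose device", once decisions on anticoagulant and antiplatelet drugs are complete.
- **How ACT is used.** Section VI includes "last ACT prior to procedural end" among the twelve variables to be screened for the hematoma logistic regression. It has no other role in the analysis.
- **How TTH is analysed.** Section VI compares continuous variables by Student's t or the Mann-Whitney test, whichever is judged appropriate. No covariate-adjusted TTH analysis and no stratified randomisation is described.
- **Design figures.** Section VI: "A sample size of 50 patients is sufficient to have >90% power", with "A standard deviation of 10 minutes is assumed" and "using a two-sided alpha of 0.05".

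**The concern.** ACT is fixed before allocation is revealed, so treatment cannot affect it and adjusting for it is legitimate. It is also a plausible influence on how long an anticoagulated patient oozes. Section IV sets no lower limit on anticoagulation and allows either heparin or bivalirudin, so ACT should vary. Section VI attributes the spread in TTH to extra compression for oozing or bleeding.

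If ACT does explain part of that spread, an unadjusted comparison leaves it in the error term. With about 25 patients per arm, the arms may also differ in mean ACT by chance, and the planned estimate would carry the resulting shift. Adding ACT only after seeing such an imbalance would be a post hoc choice, so the decision belongs in the plan now.

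**Working it through.** **Inputs.** From Section VI: N = 50, a difference of 10 min (15 vs 5), SD 10 min, two-sided alpha 0.05, no allowance for dropout. The allocation ratio is not stated; Section IV says only "sealed envelopes in randomization blocks of 25". I assume 25/25 and check 26/24, since the block size is odd. The within-arm ACT-TTH correlation r is not in the documents; I assume a range of 0 to 0.5. TTH is taken as normal with a common linear ACT effect unless stated otherwise.

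**1. The plan's own figure.** SE = 10 × √(2/25) = 2.83 min, and 10/2.83 = 3.54. Normal approximation: Φ(3.54 − 1.96) = 94.2%. Noncentral t on 48 df: 93.4% (93.3% for 26/24). For Mann-Whitney, using relative efficiency and the normal approximation: 93.3% at 0.955 and 90.8% at the worst case of 0.864. The stated power above 90% reproduces without adjustment.

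**2. With ACT in the model.** Adjusted SE = 10√(1 − r²) × √(2/25) × √(1 + 1/46), where the last factor is the expected cost of estimating one covariate. Power uses t on 47 df.

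| r | SE (min) | Power | Change from 93.4% (points) |
|---|---|---|---|
| 0 | 2.86 | 92.9% | -0.5 |
| 0.1 | 2.84 | 93.1% | -0.3 |
| 0.2 | 2.80 | 93.8% | +0.4 |
| 0.3 | 2.73 | 94.9% | +1.5 |
| 0.4 | 2.62 | 96.2% | +2.8 |
| 0.5 | 2.48 | 97.7% | +4.3 |

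Break-even: (1 − r²)(1 + 1/46) = 1 gives r² = 1/47, so |r| ≈ 0.15. Relative to 2.83, the SE changes by about +1% at r = 0, -4% at r = 0.3 and -12% at r = 0.5.

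**3. If the true effect is smaller.** Simulated power at a 6-min difference (10,000 runs per scenario), unadjusted vs adjusted: 54% vs 53% at r = 0, 55% vs 58% at r = 0.3, 55% vs 66% at r = 0.5. Under no effect, rejection rates were 4.8–5.2% unadjusted and 4.7–5.1% adjusted.

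**4. Chance imbalance.** The arm difference in mean ACT has SD √(2/25) = 0.283 in ACT SD units. The probability that it reaches 0.5 SD in either direction is 2 × [1 − Φ(0.5/0.283)] = 7.7%. The resulting shift in the TTH difference is r × 0.5 × 10 min: 1.5 min at r = 0.3 and 2.5 min at r = 0.5.

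**5. If ACT matters only in controls.** With a control-arm correlation r_c and none in the patch arm, the pooled correlation is r_c/2 if both arms have the same SD, or r_c/√2 if patch-arm TTH does not vary. For r_c = 0.4 this is 0.20 or 0.28. Holding the pooled SD at 10 min, the gain in the table is then +0.4 points or a little under +1.5.

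**The case against.** The strongest reply is that nothing is broken. An unadjusted comparison of randomised arms is valid, its type I error already averages over chance imbalances, and the stated power is met. This stands. It is weakened only in that the spare power rests on normal TTH with SD 10. Section IV has at least 5 min of compression in both arms, timed from its start, while Section VI expects a mean of 5 min in one arm. If that compression counts towards TTH, a normal distribution with SD 10 around 5 min is not attainable, so the margin above 90% is not assured.

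A second reply is that the documents hint at a weak pooled association. Section II says the patch seals without relying on coagulation, which suggests little ACT effect in that arm. This also stands; step 5 shows that the gain shrinks.

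A reader might infer that Section VI itself treats ACT as a predictor of TTH. It does not: ACT is one of twelve candidates, for hematoma. Heparin dose, INR and platelets are listed on the same footing, so choosing ACT is a judgement based on its timing and plausibility. Nor can it be said that the value is already on the CRF, because only the title of that appendix is available. What the text supports is that Section IV requires the measurement and Section VI intends to use it.

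Finally, a purely rank-based analysis would lose the effect in minutes, which is the scale on which the trial is designed. That objection is sound and shapes the fix.

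**Conclusion.** This is an efficiency and robustness improvement, not an error in the plan. A reader might conclude that precision is definitely lost, or that chance imbalance biases the trial. The documents support neither: they give no ACT-TTH association, adjustment gains nothing below |r| of about 0.15, and an imbalance reaches TTH only in proportion to r.

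What holds is that a required pre-randomisation measurement is left out of the primary comparison. Including it would cost about 0.5 to 1 point of power if it is irrelevant. It would gain about 1.5 to 4.3 points at the design effect for r from 0.3 to 0.5, and more if the true difference is below 10 min. These sizes assume 1:1 allocation, normal TTH with SD 10, and a common linear ACT effect. That ACT precedes randomisation rests on the sheath being out before closure is complete, which the sequence described in Sections IV and V implies.

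**What to change.** In Section VI, before any outcome data are seen:

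- Pre-specify one ACT-adjusted TTH analysis: an ANCOVA of TTH on study arm and the last recorded ACT before sheath removal, reporting the adjusted difference in minutes with its confidence interval.
- State that a rank-based ANCOVA will supply the p-value if TTH is skewed or heavily tied at the 5-minute floor, and write down the criterion for that in advance.
- Report the unadjusted comparison alongside, and say which of the two carries the primary p-value so that it cannot be chosen afterwards.
- Define the ACT reading. Section IV specifies a timing but says that additional readings for PCI are not recorded, so it should be clear which value is entered.
- State how a missing ACT is handled. Section IV times the reading from the first anticoagulant dose yet requires no minimum anticoagulation, so a missing value is possible.

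The cost is a few sentences and one degree of freedom, or roughly 0.5 to 1 point of power if ACT is unrelated to TTH. No extra patients are needed, and no measurement beyond the one Section IV already requires.
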